12.1 Sample Size

Total recruitment target is at least 260). These are rare patients and the aim is to recruit:

Study 1: 100-130 with EET1D plus 50-100 controls (N=~200).

Study 2: 20-40 to study plus 10-40 controls (N=30-80).

Non-diabetic controls (aged 0-6y) for Studies 1 & 2 (N=60-80).

12.2 Feasibility

This is a study to establish infrastructure to study rare patients with EET1D and MT1D. The sample size has been selected to assess feasibility rather than on the basis of statistical power. In reality with these extremely rare but potentially very interesting patients, every single patient recruited could contribute on their own to a novel discovery. Whilst accepting that we do not know what immune, beta cell or autoantibody differences we are going to find, a group of 20 v 20 gives an 80% power (alpha 0.05) to detect a difference of 10% v 50% in a proportion between the two groups and a power of 85% (alpha 0.05) to detect a 1 SD difference in a continuous variable. Each case of EET1D included in the study increases the statistical power to find new immune and genetic associations. Sometimes individual cases have specific mutations which we are now funded to test for with whole genome sequencing. Additionally, to reduce the chances of batch effects in immune and other -omics analysis, we will continue to keep case recruitment open in parallel to recruitment to the non-diabetes control cohort.

12.3 Statistical analysis

The EET1D as described are unique and findings in the various studies are difficult to predict given the novel nature of this study. The study using 100 EET1D v 100 controls gives a 90% power (alpha 0.05) to detect a difference in proportions of a binary variable of 50% v 30% and a 0.6SD difference in a continuous variable, and similarly a group of 20 v 20 gives an 80% power (alpha 0.05) to detect

a difference of 10% v 50% in the two groups and a power of 85% (alpha 0.05) to detect a 1 SD difference in a continuous variable.

13. Clinical Governance Issues

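### Protocol 12.3 states 90% power at 100 v 100 for two effects, but the power is about 83% for 50% v 30% and about 99% for 0.6 SD

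*Protocol*

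**What the plan says.** Section 12.3 of the Protocol gives one power for the 100 v 100 layout: "The study using 100 EET1D v 100 controls gives a 90% power (alpha 0.05) to detect a difference in proportions". It applies this to "a difference in proportions of a binary variable of 50% v 30% and a 0.6SD difference in a continuous variable". Neither the sidedness of alpha nor the test is stated.

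The sentence then moves, with the word 'similarly' and at the same alpha, to 20 v 20: 80% power for 10% v 50% and 85% for a 1 SD difference. Section 12.2 gives the same pair of figures ("a group of 20 v 20 gives an 80% power (alpha 0.05) to detect a difference of 10% v 50% in a proportion"). It also says that the sample size was chosen to assess feasibility and not on statistical power.

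Section 12.1 plans 100-130 EET1D participants and 50-100 controls for Study 1, so 100 is the upper end for controls.

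**The concern.** A 20-point difference in proportions around 40% and a 0.6 SD difference in means are not equally hard to detect at the same group size. One power figure for both is therefore suspect on sight. All the inputs needed to check it stand in the sentence, and the result does not depend on which comparators make up the 100 controls.

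The primary outcome in section 3.2 consists of C-peptide and islet autoantibodies. The Protocol does not define autoantibody positivity as a binary endpoint, but that is the natural way to analyse it, so the figure for proportions bears on a primary outcome. If that figure is too high, a null Study 1 comparison will look more reassuring than it is. If the continuous figure is too low, the Protocol undersells what the C-peptide comparison can show.

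**Working it through.** **Inputs, all from section 12.3:** n = 100 per group; alpha 0.05, sidedness not stated; p1 = 0.50 and p2 = 0.30; standardised difference d = 0.6; stated power 90% for both. The 20 v 20 figures serve to infer the sidedness.

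**1. Proportions, 100 v 100, two-sided.** Power = Φ[(|p1 − p2| − z·SE0)/SE1], with SE0 the pooled and SE1 the unpooled standard error.
- SE0 = √(2 × 0.4 × 0.6/100) = 0.0693
- SE1 = √((0.25 + 0.21)/100) = 0.0678
- (0.20 − 1.96 × 0.0693)/0.0678 = 0.947, so power = **82.8%**

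Other two-sided methods give 83.9% (unpooled variance), 82.9% (arcsine), 83.2% (exact power of the chi-square test), 78.8% (continuity-corrected) and 79.2% (Fisher). None comes close to 90%.

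**2. Continuous variable, 100 v 100, two-sided.** Power ≈ Φ(d√(n/2) − 1.96) = Φ(0.6 × 7.071 − 1.96) = Φ(2.283) = 98.9%. With the noncentral t it is **98.8%**.

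**3. Would a one-sided test reproduce the 90%?** Replace 1.96 by 1.645.
- 50% v 30%: (0.20 − 1.645 × 0.0693)/0.0678 = 1.269, giving 89.8%. This matches.
- 0.6 SD: 99.5%. This is further away.

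No single convention gives 90% for both effects.

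**4. Which convention do the 20 v 20 figures follow?**

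| Effect, 20 v 20 | Stated | Two-sided | One-sided |
|---|---|---|---|
| 10% v 50% (pooled normal) | 80% | 81.3% | 89.2% |
| 1 SD (t-test) | 85% | 86.9% | 92.8% |

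For the first row: SE0 = √(2 × 0.3 × 0.7/20) = 0.1449, SE1 = √((0.09 + 0.25)/20) = 0.1304, and (0.40 − 1.96 × 0.1449)/0.1304 = 0.889, giving 81.3%. Both stated figures lie within 2 points of the two-sided result and well below the one-sided result.

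**5. What 90% would require, two-sided.**
- 50% v 30%: n = [1.96√(2 × 0.4 × 0.6) + 1.2816√(0.25 + 0.21)]²/0.20² = 124 per group, or 134 with continuity correction.
- 0.6 SD: 59 per group by the normal formula; 60 per group gives 90.3% by the t-test.
- Detectable with 90% power at 100 v 100: 50% v 27.9% (50% v 28% has 89.7%), and 0.46 SD.

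**6. Across the range planned in section 12.1.** 130 v 100 gives 87% for 50% v 30%. 100 v 50 gives 65% to 67%, depending on which group has the 50%, and 93% for 0.6 SD.

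**The case against.** The strongest defence is that nothing depends on the number. Section 12.2 says that the size was set on feasibility and that the team does not know what differences it will find. Section 4.1 adds that rarity makes power calculations very difficult. The 50% v 30% contrast is illustrative, and no recruitment target or decision follows from the 90%. This stands, and it limits the consequence. It does not make the printed figure correct.

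Second, a design with 98.8% power for 0.6 SD does have at least 90%. This also stands: that half of the statement is imprecise but cautious. The same reading cannot cover 50% v 30%, where 90% is an overstatement.

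Third, sidedness is not stated, and a one-sided test gives 89.8% for the proportions. For that figure alone, the fault could be an undeclared convention rather than a miscalculation. But the 20 v 20 figures in the same sentence then fail to reproduce. That inference depends partly on the test: two-sided Fisher gives 74.2% for 10% v 50% at 20 v 20, not 80%. The 1 SD figure does not depend on the choice of test for proportions, and it too points to two-sided testing. For the same reason the fair comparison at 100 v 100 is the uncorrected one, about 83%. The 79.2% from Fisher is the lower figure if that test were used.

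**Conclusion.** The concern holds. At 100 v 100 and two-sided alpha 0.05, power for 50% v 30% is about 83%, not 90%, so the chance of missing such a difference is about 17% (21% with Fisher) instead of 10%. Power for 0.6 SD is about 99%. The stated value is about 7 points too high for the first effect and about 9 points too low for the second, so rounding cannot explain it. On the two-sided reading, 90% for 50% v 30% is not reached anywhere in the Study 1 range of section 12.1.

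This assumes a single unadjusted two-group comparison with independent participants. The two-sided reading is inferred from the 20 v 20 figures. Under a one-sided test the figure for proportions would be right and the figure for 0.6 SD would still be wrong. The error changes what the Protocol claims for Study 1, not its design or size.

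**What to change.** Replace the 100 v 100 statement in section 12.3 with wording to this effect:

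*With 100 EET1D and 100 controls and a two-sided alpha of 0.05, power is 83% for 50% v 30% and 99% for a 0.6 SD difference; 90% power corresponds to about 50% v 28% and to 0.46 SD.*

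State in sections 12.2 and 12.3 that alpha is two-sided throughout, and name the tests (uncorrected chi-square for proportions, t-test for means). The 20 v 20 figures can then stay as they are.

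Because section 12.1 allows as few as 50 controls, it would help to add that 100 v 50 gives about 65% to 67% for 50% v 30% and 93% for 0.6 SD. Otherwise the corrected 83% describes only the upper end for controls.

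The cost is one sentence, or two with the addition, and one figure becomes less favourable. No patients, procedures or analyses change.

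### Section 12.3 gives 90% power at 100 v 100 for both 50% v 30% and 0.6 SD; two-sided, the figures are about 83% and 99%

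*Protocol*

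**What the plan says.** Section 12.3 of the protocol states that "100 EET1D v 100 controls gives a 90% power (alpha 0.05) to detect a difference in proportions of a binary variable of 50% v 30"%; it extends that figure to a 0.6 SD difference. One power, 90%, covers both a binary and a continuous outcome. The same sentence repeats two figures from section 12.2: "a group of 20 v 20 gives an 80% power (alpha 0.05) to detect a difference of 10% v 50"%, and 85% power for a 1 SD difference with the same 20 per group. Neither section names a test or says whether alpha is one- or two-sided.

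Section 12.2 explains that numbers were chosen for feasibility and not for power, and concedes that "we do not know what immune, beta cell or autoantibody differences we are going to find".

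The number of Study 1 controls is not given consistently. Section 12.1 has "Study 1: 100-130 with EET1D plus 50-100 controls (N=~200"), whereas the synopsis and section 4.1 both give 100 controls.

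**The concern.** At a fixed 100 per group, 50% v 30% and 0.6 SD are effects of quite different standardised size, so one power figure is unlikely to fit both. The usual two-sided formula gives well under 90% for the proportions and well over 90% for the means.

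The overstated half matters more. Islet autoantibodies are part of the primary endpoint (section 3.2), and positivity is naturally analysed as a proportion. These are the only power figures for the 100 v 100 comparison. A reader who relies on them would take the risk of missing a true 50% v 30% difference to be about half what it is.

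**Working it through.** **Inputs.** From section 12.3: 100 per group, alpha 0.05, rates 50% and 30%, a difference of 0.6 SD, stated power 90%. From sections 12.2 and 12.3: 20 per group, 10% v 50% at 80%, and 1 SD at 85%. From section 12.1: 50-100 controls. Sidedness is not given and has to be inferred. A figure counts as reproduced here if it falls within 2 points of the stated one.

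**Step 1: which convention does the sentence use?** For proportions (pooled z), power = Φ[(|p1 − p2| − z·SE0)/SE1], with SE0 = √(2·p̄(1 − p̄)/n) and SE1 = √((p1(1 − p1) + p2(1 − p2))/n).

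For 20 v 20 and 10% v 50%: p̄ = 0.30, SE0 = √(2·0.30·0.70/20) = 0.1449, SE1 = √((0.09 + 0.25)/20) = 0.1304.
- Two-sided (z = 1.960): (0.40 − 0.2840)/0.1304 = 0.889, power 81.3%.
- One-sided (z = 1.645): (0.40 − 0.2384)/0.1304 = 1.240, power 89.2%.

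For 20 v 20 and 1 SD (noncentral t, noncentrality 1/√(2/20) = 3.162): 86.9% two-sided and 92.8% one-sided.

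The stated 80% and 85% are reproduced two-sided. Neither is reproduced one-sided.

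**Step 2: 100 v 100, 50% v 30%, two-sided.** p̄ = 0.40, SE0 = √(2·0.40·0.60/100) = 0.0693, SE1 = √((0.25 + 0.21)/100) = 0.0678. Then (0.20 − 1.960·0.0693)/0.0678 = 0.947, power 82.8%.

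| Method | Two-sided | One-sided |
|---|---|---|
| Pooled z | 82.8% | 89.8% |
| Unpooled z | 83.9% | 90.4% |
| Arcsine | 82.9% | 89.7% |
| Chi-square, full enumeration | 83.2% | 89.6% |
| Fisher's exact, full enumeration | 79.2% | 86.6% |
| Continuity-corrected z | 78.8% | 86.9% |

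No two-sided method comes within 2 points of 90%. A true 90% needs 124 per group by pooled z, or 134 with continuity correction.

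**Step 3: 100 v 100, 0.6 SD.** Noncentrality = 0.6/√(2/100) = 4.243. Power is 98.8% two-sided and 99.5% one-sided, so neither gives 90%. About 60 per group would give 90% for 0.6 SD.

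**Step 4: what 100 v 100 detects at 90%, two-sided.** About 50% v 28% (or 52% v 30%) for a proportion, and 0.46 SD for a mean.

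**Step 5: the lower end of section 12.1, 100 v 50.** Pooled z gives 65.1% for 50% v 30%, or 66.7% if the smaller group has the 50% rate. For 0.6 SD, power is 93.1%.

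**The case against.** *The sample size does not rest on power.* Section 12.2 says so, and section 4.1 adds that rarity makes both recruitment forecasts and power calculations difficult. No target or decision rule uses the 90%. This stands. It makes the correction minor but does not make the figure right.

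*Alpha may be one-sided.* The protocol does not say, and one-sided 0.05 gives 89.8% for 50% v 30%, in line with the stated 90%. The two-sided reading is therefore an inference. But one-sided breaks both 20 v 20 figures and moves 0.6 SD to 99.5%. It also sits badly with the admission in section 12.2 that the nature of the differences is unknown.

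*The 0.6 SD figure is safe.* Agreed: a design with 99% power does have at least 90%. That half is imprecise, not misleading in a harmful direction.

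Three stronger readings are tempting, and the documents do not support them:
- **That an observed 20-point difference could be non-significant and be misread.** Power concerns a true difference. An observed 50/100 v 30/100 gives z = 0.20/0.0693 = 2.89, p about 0.004, so it would be significant.
- **That the 100 controls are shared between older-onset T1D and NDM, so that no contrast is 100 v 100.** Section 4.2 lists both groups under Study 1, but nowhere is the 100 said to be divided. Section 3.2 gives the Study 1 aim as a comparison with older-onset T1D, and section 4.1 draws those comparators from an existing research cohort.
- **That the 50-control lower limit makes section 12.3 wrong.** The sentence is explicitly conditional on 100 v 100. The range in section 12.1 is a separate inconsistency. Pairing 100 cases with 50 controls totals 150, against the approximate 200 on the same line; 130 v 70 would total 200 and give about 79%.

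**Conclusion.** The statement is wrong as written, and the correction is minor. At two-sided 0.05, 100 v 100 gives about 83% power for 50% v 30% (79% by Fisher's exact test) and about 99% for 0.6 SD. The chance of missing a true 50% v 30% difference is therefore 17-21%, where the protocol implies 10%.

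The conclusion rests on a two-sided test, inferred from the 20 v 20 figures. Had one-sided been meant, the binary figure would be about right, but the 0.6 SD figure and both 20 v 20 figures would not. None of the conventions checked gives 90% for both halves of the clause. It would be wrong to infer that the study is too small for its purpose, since its size was justified on feasibility.

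**What to change.** Reword section 12.3 along these lines: *100 v 100 gives about 83% power (two-sided alpha 0.05) for 50% v 30% and about 99% for a 0.6 SD difference; at 90% power the detectable differences are about 50% v 28% and 0.46 SD.* If Fisher's exact test is intended for the proportions, give 79% in place of 83% and recompute the detectable difference for that test.

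Reconcile the number of Study 1 controls between section 12.1 (50-100) and the synopsis and section 4.1 (100). If fewer than 100 are kept, add the lower power: about 65-67% for 50% v 30% at 100 v 50.

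The cost is wording only, at the next amendment. One stated figure becomes less favourable, and no recruitment number changes because of the corrected power.

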13.1 Compliance

The CI will ensure that the study is conducted in compliance with the principles of the Declaration of Helsinki (2013), the principles of GCP and in accordance with all applicable regulatory requirements including but not limited to the UK Policy Framework for Health and Social Care Research (2020) and the Medicines for Human Use (Clinical Trial) Regulations 2004, as amended in 2006, 2008 and 2009 and any future relevant or replacement EU Regulations, Trust and R&D Office policies and procedures and any subsequent amendments.

13.2 Ethical Considerations

This protocol and any subsequent amendments, along with any accompanying material provided to the patient in addition to any advertising material, will be submitted by the Chief Investigator to an independent UK Research Ethics Committee (REC) and the Health Research Authority (HRA). Written REC and HRA approvals must be obtained and subsequently submitted to R&D to obtain Final Trust Approval.

All correspondence with the REC will be retained in the Trial Master File/Investigator Site File. Annual progress, safety reports and a final report at conclusion of the study will be submitted to the Sponsor and the REC. All protocol amendments will be submitted to the Sponsor, REC and Regulatory Authorities for approval. The CI will notify the REC of the end of the study and, should the study end prematurely, the CI will notify the REC, including the reasons for the premature termination.

Clinicians based worldwide will be involved in recruiting participants outside the UK and will operate under their own site's Institutional Review Board (IRB) approval.

14. Quality Control and Quality Assurance

14.1 Monitoring

Monitoring of this study will ensure compliance with Good Clinical Practice. The Investigators will permit monitoring, audits, REC review, and regulatory inspections by providing the Sponsor(s), Regulators and REC direct access to source data and other documents (eg patients' case report forms, consent forms, etc). Periodic remote monitoring will be carried out by the CI's study team and the Sponsor. Consent will be obtained to permit access to data by external staff responsible for monitoring and auditing the study as a requirement of participating in the study.

Remote monitoring of recruitment activities at all sites will be carried out periodically by the study management team (on behalf of the CI & Sponsor) by exploring data, consent forms, delegation logs & recruitment logs copied to the CI in accordance with the study SOPs.

To facilitate this remote monitoring, and ensure timely and efficient transfer of data to the central study database, recruiting sites will be required to:

- Transfer scanned (PDF) copies of completed CRFs (data collection forms), consent forms and biochemistry results (via secure nhs.net email) to the CI site within 5 working days of the study visit.
- Monitoring reports will be stored in the study Trial Master File and copied to the Sponsor.

NHS Indemnity will apply to UK-based sites.

14.2 Audit and Inspection

A study may be identified for audit by any method listed below:

- i) A project may be identified via the risk assessment process.
- ii) An individual investigator or department may request an audit.

- iii) A project may be identified via an allegation of research misconduct or fraud or a suspected breach of regulations.
- iv) Projects may be selected at random. The UK Department of Health states that Trusts should be auditing a minimum of 10% of all research projects.
- v) Projects may be randomly selected for audit by an external organisation (e.g. MHRA). Internal audits will be conducted by a Sponsor's representative.

14.3 Amendments

Under the Medicines for Human Use (Clinical Trials) Regulations 2004, the Sponsor may make a non-substantial amendment at any time during a trial. If the Sponsor wishes to make a substantial amendment to the REC application or the supporting documents, the Sponsor will submit a valid notice of amendment to the REC for consideration. The REC will provide a response regarding the amendment within 35 days of receipt of the notice. It is the Sponsor's responsibility to decide whether an amendment is substantial or non-substantial for the purposes of submission to the REC. Amendments will be notified to NHS R&D departments of participating sites to assess whether the amendment affects the NHS permission for that site. The amendment history will be tracked in the Trial Master File/Investigator Site File to identify the most recent protocol version.

14.4 Financial and other competing interests for the Chief Investigator, PIs at each site and committee members for the overall study management

No financial or other competing interests to disclose.

14.5 Indemnity

NHS Indemnity will apply to UK participants and public liability insurance is provided by the University of Exeter.

14.6 Protocol compliance

Protocol deviations, non-compliances, or breaches are departures from the approved protocol. Accidental protocol deviations can happen at any time and must be adequately documented on the relevant forms and reported to the Chief Investigator and Sponsor immediately. Deviations from the protocol which are found to frequently recur are not acceptable, will require immediate action and could potentially be classified as a serious breach.

14.7 Non-Compliance

Defined as a noted systematic lack of both the CI and the study staff adhering to SOPs/protocol/ ICH-GCP and UK regulations, which leads to prolonged collection of deviations, breaches or suspected fraud.

These non-compliances may be captured from a variety of different sources including monitoring visits, CRFs, communications and updates. The Sponsor will maintain a log of the non-compliances to ascertain if there are any trends developing which need to be escalated. The Sponsor will assess the non-compliances and action a timeframe in which they need to be dealt with. Each action will be given a different timeframe dependent on the severity. If the actions are not dealt with accordingly, the R&D will agree an appropriate action, including an on-site audit.

15. Study Committees

The EXE-T1D Study Management Group (SMG) will be defined as the CI, Co-investigators, and Project Manager, who will meet/communicate regularly to ensure all practical details of the study are progressing and working well and that everyone within the study understands them correctly.

16. Access to the final study dataset

The Exeter study team will have access to the final dataset. Of the multiple analyses done during the study, relevant co-investigators for each analysis (e.g. RNAseq for [name]) will have access to the datasets they have contributed to.

17. Public and Patient Involvement

This study was born out of the CI's direct contact with patients referred to the Exeter Molecular Genetics Laboratory from around the world with a diagnosis of diabetes in the first 12 months of life. They were suspected to have a possible genetic diagnosis for their diabetes but were shown to have likely Type 1 diabetes. The "absence" of a genetic diagnosis has been disappointing for some patients, and has prompted them to question why they have developed diabetes so early when the immune system is still developing. In addition, some patients and parents have asked why some people have developed T1D near birth whereas their affected siblings or parents have been diagnosed at much more typical ages. Both patients, relatives and clinicians have been in agreement that there would be significant benefit to knowing why and how T1D can present so young and whether understanding this could help with treatment or prevention.

A particular focus in this study design has been appreciation of the difficulty in collecting blood samples from young children. We have, therefore, specifically designed the study around a protocol that requires minimal blood samples that can usually be collected at the same time as routine clinical tests with no additional venepuncture, and have used a novel approach to collection, postage and analysis of fingerprick blood samples that again requires no additional fingerpricks to the patient's standard blood glucose monitoring.

This work is part-funded by a patient-focused charity, Diabetes UK that represents people with Diabetes in the UK, and The Leona M. and Harry B. Helmsley Charitable Trust; both charities consider this to be an important area of research.

The study team also has access to the user representative group of the NIHR Exeter Clinical Research Facility (ECRF). In keeping with the NHS Patient Carer and Public Involvement (PCPI) strategy, the Exeter CRF invites user representatives to contribute to the development of various projects within its portfolio. These individuals have agreed to maintain contact and regular meetings have been established at which researchers discuss the development of current projects within the Exeter CRF. Additional PPI has been conducted with parents of healthy young children, paediatricians and paediatric anaesthetists to agree an optimal strategy to recruit a cohort of healthy non-diabetic controls.

18. Publication Policy

On completion of the study, the data will be analysed and tabulated and a Final Study Report will be prepared and submitted to the Funder, Sponsor and REC. Results will be written up and submitted for publication in a peer-reviewed journal(s). Abstracts will be submitted to national and international conferences. Results will be presented to clinical colleagues at regular in-house meetings.

Written information in the form of a letter/newsletter outlining the key findings of the study will be posted on the study website.

- The University of Exeter owns the data arising from the study.
- There are no time limits or review requirements on the publications.
- The Funder will be acknowledged within publications but does not have review or publication rights.
- After the Final Study Report has been compiled, participants may specifically request results from their PI.
- The study protocol has been registered with ClinicalTrials.gov: NCT03369821.

19. References

